The Cumulative Illness Rating Scale for Geriatrics (CIRS-G)² will be used to assess baseline illness severity and comorbidity. We will use data from the medical record to complete the CIRS-G scale. The CIRS-G manual has specific criteria for scoring illness severity. We have extensive prior experience in use of the CIRS-G in a variety of research settings. We will use CIRS-G total score as an independent variable of baseline comorbidity in data analyses.

Medications received during each data collection period will be identified from the electronic medical record and a structured medication interview. Medications will be coded by class using a coding system we developed in prior work. We will focus on sedating medications that may affect sleep. With a methodology we used in prior research,³ sedating medication use will be summarized categorically (i.e., was a certain class of sedating medication received, and at what time); then daily dose(s) will be converted to total daily equivalences by class according to standardized criteria. Because of the intention to treat analysis, major outcomes will be compared between the intervention and control groups regardless of medication status. However, the medication variables (e.g., total daily equivalence of sedating medication at each time point) may be explored as potential covariates in outcome analyses, and use/nonuse of sedating medications may be considered in subgroup comparisons (e.g., subgroup analysis in only participants who did or did not receive sleeping pills).

Questionnaires (Data Collected from Participants)

- Descriptive information will be collected in all participants, including age, gender, ethnicity, **marital status**, and other demographic characteristics.
- Cognitive status

The Mini-Mental State Examination (MMSE) will be used to screen consented individuals for inclusion and to measure baseline cognitive status.⁴ This scale assesses orientation, registration, attention/calculation, recall, language and construction, and has standard instructions. MMSE scores range from 0 to 30, where higher scores indicate better mental status. A score below 24 is consistent with dementia or delirium. MMSE total score will be used in determining study eligibility (i.e., MMSE score < 24 is an exclusion criteria) and as an independent variable of cognitive status in analyses.

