1	1	30 minutes	Introduction; general sleep and OSA education
2	2	30 minutes	Sleep across the lifespan, general health education
3	3	30 minutes	Sleep and health

4	4	30 minutes	Daytime relaxation techniques
6	5	30 minutes	Daytime stress reduction

Post-Treatment and Follow-up Assessments

Post-treatment and follow-up assessments will be performed by research personnel blinded to group assignment. Participants who can no longer travel to VA GLAHS (e.g., moved away, too ill) will be visited at their living location (if < 30 miles away) or interviewed by telephone (if ≥ 30 miles away). Veterans will receive \$25 for each assessment for a possible total of \$100 (i.e., baseline, post-treatment, 3-month and 6-month).

Table 4: Time Points for Data Collection and Measures Used

	Baseline	Post-tx	3-mo	6-mo	12-mo
Data Collected by Research Staff					
Blood sample: assayed for proinflammatory cytokines and corresponding acute-phase proteins (i.e., CRP, TNF α , IL-6, IL-8, and IL-10)	✓	✓	✓	✓	
Medication review	✓	✓	✓	✓	
Data Collected from Participants					
Demographic data	✓				
Mini-Mental State Examination (MMSE)	✓				
Hopkins Verbal Learning Test – Revised (HVLT-R)	✓	✓	✓	✓	
Digit Symbol Substitution	✓	✓	✓	✓	
Trails A and B	✓	✓	✓	✓	
Forward and Backward Digit Span	✓	✓	✓	✓	
Letter-Number Sequencing	✓	✓	✓	✓	
Control Oral Word Association (COWA)	✓	✓	✓	✓	
Geriatric Pain Measure (GPM) intensity subscale	✓	✓	✓	✓	
Restless Leg Syndrome scale (RLS)	✓				
Pittsburgh Sleep Quality Index (PSQI)	✓	✓	✓	✓	✓
Insomnia Severity Index (ISI)	✓	✓	✓	✓	✓
Epworth Sleepiness Scale (ESS)	✓	✓	✓	✓	✓
Patient Health Quest. depression module (PHQ-9)	✓	✓	✓	✓	
12-item Short-form Health Survey (SF-12v2)	✓	✓	✓	✓	
EuroQol-5D scale (EQ-5D)	✓	✓	✓	✓	
PHQ GAD	✓	✓	✓	✓	
PC-PTSD	✓				
Caregiving questions	✓	✓	✓	✓	
Dysfunctional Beliefs & Attitudes about Sleep (DBAS-16)	✓	✓	✓	✓	
PAP Self-efficacy, Knowledge and Decisional Balance Index subscales	✓	✓	✓	✓	
Data from Participant Monitoring					
Wrist actigraphy	✓	✓	✓	✓	
PAP adherence		✓	✓	✓	✓
Follow-up Data from Participant/ Record Review					
Sleep clinic visits		✓	✓	✓	

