We expect that the group by time analysis of covariance for the sleep variables will show a difference between groups, and post-hoc analyses will show increased nighttime sleep efficiency and improved self-reported sleep (indicated by lower PSQI scores) in the intervention group compared to the control group. Following review of graphical representation of our longitudinal results (on main outcome measures), we will use repeated measures ANCOVA models to test both linear and nonlinear (i.e., quadratic) differential changes over time. Post-hoc tests within each time point (using Tukey type 1 error control) will be conducted. We expect there will be no difference between intervention and control groups at baseline, but differences will be present at follow-up. Other participant characteristics will be considered as possible covariates to reduce bias in our estimate of treatment effects and to increase precision. The major covariates that we expect to consider are age, cognition (estimated by MMSE) and comorbidity (estimated by CIRS-G). Other covariates we will consider include specific diagnoses and medications that may interfere with sleep, and measures of the intervention process (DBAS-16 scores, Self-efficacy, Knowledge and Decisional Balance Index subscales).

Sample size calculations were performed for each of the main outcome variables using reported effect sizes and/or calculated effect sizes from reported sample means and standard deviations reported in the literature in prior studies of CBT-I for insomnia and behavioral PAP adherence interventions in outpatient adults (see Table 5). Prior literature indicates that CBT-I is an extremely potent intervention for insomnia, and the studies typically have large effect sizes and small samples. Some caution is warranted, however, since efficacy studies usually employ tightly controlled ‘ideal’ treatment conditions, which also yield larger effect sizes

than effectiveness studies with more ‘real world’ conditions. Regardless of these issues, even the most conservative estimates of effect size from the literature suggest we will have an adequate sample size to test our sleep outcomes. A recent meta-analysis of trials of PAP adherence interventions published as a Cochrane review was used in estimating sample size for the PAP adherence component of our intervention.^{Error! Bookmark not defined.} this analysis suggests we will have an adequate sample size to test our PAP adherence outcomes.

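### Sedating-medication covariates, and possibly subgroups, are not restricted to baseline use; conditioning on follow-up use can bias the comparison if treatment changes that use and use is related to sleep

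*Combined protocol and SAP*

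**What the plan says.** The relevant text is in the combined protocol and SAP, under Medical Chart Review, in the item on comorbidity, illness severity and medications.

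- **Timing of the data.** "Medications received during each data collection period will be identified from the electronic medical record and a structured medication interview". Table 4 schedules the medication review at baseline, post-treatment, 3 months and 6 months.
- **Main comparison.** Because the analysis is by intention to treat, "major outcomes will be compared between the intervention and control groups regardless of medication status".
- **Covariates.** The next sentence opens an exception. The medication variables that may be explored as covariates in outcome analyses include the "total daily equivalence of sedating medication at each time point".
- **Subgroups.** In the same sentence, "use/nonuse of sedating medications may be considered in subgroup comparisons", with the example of a "subgroup analysis in only participants who did or did not receive sleeping pills". No time point is given.
- **Hypothesis 1.** The Analysis Plan names age, MMSE and CIRS-G as the major covariates, then adds: "Other covariates we will consider include specific diagnoses and medications that may interfere with sleep, and measures of the intervention process". No time point is given here either.

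By contrast, the CIRS-G and MMSE scores are tied explicitly to baseline status where they are introduced. Medication is not.

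**The concern.** The trial treats insomnia. Whether a participant takes a sleeping pill at 3 or 6 months may depend on how well that participant is sleeping, and may therefore depend on the assigned arm. Users in one arm need not resemble users in the other, and the same goes for non-users. Randomization does not protect a comparison made within those groups, or adjusted for follow-up dose.

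The PSQI raises a further problem that needs no assumed rates. The protocol's description of the scale includes use of sleeping medication among the things it measures, the total score is analysed, and it is a Hypothesis 1 outcome. Adjusting or splitting the PSQI by concurrent sleeping-pill use conditions on part of the outcome itself.

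At stake is any published result in users or non-users, and any adjusted version of the main results that includes follow-up medication. Hypothesis 1 says covariates are considered partly to reduce bias. A follow-up medication covariate can introduce it. The safeguards under Potential Shortcomings in the Proposed Analysis (factor analysis, repeated split samples) address overfitting, which is a different problem.

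**Working it through.** The plan states no figure on this point, so there is nothing of its own to reproduce. What follows is an illustration.

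**Inputs from the documents.** Sample size estimates: 120 randomized with 15% loss, so 120 × .85 = 102, or 51 per group at 6 months. Table 5: planned effect of .60 for actigraphy sleep efficiency. Two-sided .05 level.

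**Assumptions (the documents give no values).** A follow-up use rate in each arm, and a correlation r between the propensity to use sedating medication and worse sleep. Treatment has no effect on the sleep outcome (SD 1, higher is better). A participant is a user when a standard normal propensity exceeds an arm-specific threshold z, so treatment acts on use by shifting that threshold.

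**Formulas.** With use rate p and normal density φ(z) at the threshold, mean propensity is φ(z)/p in users and −φ(z)/(1−p) in non-users. The bias, intervention (1) minus control (0), is:

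- non-users: r × [φ(z1)/(1−p1) − φ(z0)/(1−p0)]
- users: −r × [φ(z1)/p1 − φ(z0)/p0]

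**Densities.** p = .40: φ = .3863. p = .30: φ = .3477. p = .20: φ = .2800.

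**40% control, 20% intervention.**

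- Non-users: .2800/.80 − .3863/.60 = .350 − .644 = −.294. Times r = .3 and .5: −.09 and −.15 SD.
- Users: −(.2800/.20 − .3863/.40) = −(1.400 − .966) = −.434. Times r: −.13 and −.22 SD.

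**40% control, 30% intervention.**

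- Non-users: .3477/.70 − .3863/.60 = .497 − .644 = −.147. Times r: −.04 and −.07 SD.
- Users: −(.3477/.30 − .3863/.40) = −(1.159 − .966) = −.193. Times r: −.06 and −.10 SD.

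**Equal use in both arms.** Both brackets are zero, so the bias is zero at every r. It is also zero if r = 0, whatever the rates.

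**Adjusted model.** At 40% against 20%, 51 per arm gives 20.4 control and 10.2 intervention users, and 30.6 and 40.8 non-users. The variances of the two differences are about 1/20.4 + 1/10.2 = .147 and 1/30.6 + 1/40.8 = .057. Weighting the r = .5 biases by inverse variance: (−.147/.057 − .217/.147) / (1/.057 + 1/.147) ≈ −.17 SD. This adjusts for use yes/no; the plan's covariate is dose, so it is a guide only.

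**Simulated false-positive rates, 51 per group, two-sided .05.**

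| Use, control vs intervention | r | Non-users | Users | Adjusted for use | Unadjusted ITT |
|---|---|---|---|---|---|
| 40% vs 40% | .5 | 5% | 4% | 5% | 5% |
| 40% vs 30% | .3 | 5% | 5% | 5% | 4% |
| 40% vs 20% | .5 | 10% | 9% | 15% | 5% |
| 50% vs 20% | .7 | 29% | 28% | 50% | 5% |

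The last row is a deliberately extreme case. Its biases are −.31 SD (non-users), −.42 SD (users) and −.35 SD (adjusted).

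**The case against.** The strongest reply has five parts.

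1. **The main result is protected.** The plan says outcomes are compared whatever the medication status, and the disputed analyses are optional. This stands. In the illustration the unadjusted comparison has no bias in any scenario. It does not settle the matter, because Hypothesis 1 lets medications into adjusted models of the same outcomes.

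2. **The subgroup sentence may mean baseline use.** This also stands: no time point is given, and a baseline subgroup would be sound. A reader might infer that the plan defines subgroups by follow-up use, but the text does not say so. Only the covariate is explicitly tied to every time point. The Hypothesis 1 list is undated too. Its heading of participant characteristics fits baseline variables, but it also contains intervention process measures, which are collected at follow-up as well.

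3. **Nothing says treatment changes medication use.** Correct. Table 2 lists no medication component. The mechanism is plausible in an insomnia trial, but it is an assumption. A reader might infer that these comparisons are biased even if treatment does nothing at all. That is not so: if treatment leaves use unchanged, the bias is zero.

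4. **The size is modest.** At 40% against 20%, the standard errors are about √.147 = .38 SD in users and √.057 = .24 SD in non-users, larger than the biases of .13 to .22 and .09 to .15. Imprecision dominates the subgroups, and the sample-size text already admits that subgroup samples are small. The adjusted model uses all participants and is less sheltered by this.

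5. **The direction is not fixed.** A reader might infer that adjusting for follow-up dose removes part of a true benefit. The illustration assumes no true effect, so it cannot show that. If pills improve sleep and treatment lowers their use, adjustment could enlarge the estimated benefit.

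**Conclusion.** The point holds in limited form. For covariates, the plan explicitly permits adjustment for a post-randomization variable. For subgroups and for the Hypothesis 1 list, it leaves the time point open. Bias in the absence of an effect on sleep requires two things together: treatment changes sedating-medication use, and use is related to the sleep outcome.

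Under the assumed rates and correlations, the subgroup bias runs from about .04 to .22 SD against the intervention, compared with a planned actigraphy effect of .60. At the mild end the error rate stays near its nominal level. Size and sign rest on those assumptions, including that treatment lowers use. The PSQI overlap follows from the protocol's own description of the scale and needs no such figures.

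This does not call the unadjusted intention-to-treat result into question. It is a nearly free improvement to optional analyses.

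**What to change.** In the medication paragraph under Medical Chart Review and in the covariate list under Hypothesis 1:

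- Define medication covariates and subgroups by sedating use and dose at baseline, before randomization.
- Test each medication subgroup through a group by baseline-use interaction, not by separate tests in users and non-users.
- Report sedating-medication use and dose at follow-up as an outcome, by arm.
- If an analysis conditioned on follow-up use is still wanted, keep it, but label it non-randomized and exploratory. For the PSQI, note that the scale itself counts sleeping-medication use.

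The cost is a few sentences of wording. The baseline medication review is already in Table 4, so no new data, visits or participants are needed.

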We will use a two-step process to recruit participants for this study. In the first step of recruitment, we will screen for insomnia among Veterans aged 50 years and older who are referred to the VA GLAHS sleep clinics to rule out OSA (based on the reason for referral to the sleep clinic indicated on the electronic consultation form). At our institution, the majority of individuals referred to sleep clinics are referred for possible OSA, and most referred patients receive an ambulatory (i.e., in-home portable) sleep study (rather than a study in the sleep laboratory) to test for OSA. However, we will enroll participants regardless of the location (in-home or in-laboratory) of their OSA testing. Currently, there is a 3-4 week wait for an ambulatory sleep study; the wait for an in-laboratory study is > 4 weeks. We will mail a letter to these Veterans when their referral to sleep clinic is received to briefly introduce the research, and to offer them a mechanism to “opt-out” of further contact by our research team, using a methodology previously approved by our institutional review board. For patients who do not opt out within 7 days of receiving the letter, our staff will contact them by telephone (or in-person if preferred by the Veteran) to complete a brief screening measure for insomnia. The insomnia screener is a brief questionnaire that summarizes key diagnostic criteria for insomnia according to ICSD2^{Error! Bookmark not defined.} (see Appendix 1), which we developed, tested and currently use in our ongoing study of CBT-I to treat insomnia in older outpatient Veterans (VA HSRD IIR 08-296, PI [name]). Veterans who meet diagnostic criteria for insomnia will be invited to participate in the study and an in-person visit will be scheduled to explain study procedures, obtain written informed consent, and begin assessment procedures. After consent, the Veteran will be sent home with a wrist actigraph to wear for 7 days and nights as an objective measure of sleep/wake patterns. Additional baseline data (e.g., demographic information, subjective measures of sleep, assessment of depressive symptoms, medical comorbidity, health-related quality of life) will be collected using structured, validated questionnaires (see below). In addition, one blood sample will be collected. All research data will be collected by trained research staff. All study visits will be performed in dedicated office space, separate from the sleep clinics. Separate research staff will perform assessment versus intervention activities, in order to maintain blinding of both clinic staff and research assessment staff.

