
In the second step of recruitment, consented Veterans who have completed baseline testing, are diagnosed with OSA (based on sleep clinic physicians interpretation of sleep study results) and are prescribed PAP therapy (by sleep clinic clinicians) will be reminded of study procedures, and invited to participate in the randomized controlled trial. Inclusion criteria will include: 1) age \geq 50 years, 2) meeting ICSD2 diagnostic criteria for insomnia, and 3) diagnosis of OSA with an AHI \geq 15 and prescription of PAP therapy. Exclusion criteria for randomization will include the following: 1) refusal to schedule an appointment to begin PAP therapy, 2) a Mini-mental State Examination (MMSE) score < 24 (used to screen for significant cognitive impairment), and 3) a history of mania (which is a contraindication for the sleep restriction component of CBT-I), major psychopathology (e.g., psychosis) or a psychiatric hospitalization within the prior two years.

- Randomization

Participants will be randomized to the intervention or control group using a randomized block design based on results from the OSA testing, to increase the likelihood of comparable severity of OSA in both groups. Specifically, individuals will be categorized based on AHI < 30 or AHI \geq 30. Consented participants will be randomized as a block within each category (similar to block randomization techniques we have used in prior research). Available randomization software (e.g., Random Allocation Software, Paradigm) which allows for block randomized sequences for parallel group randomized trials will be used to assign participants to the intervention or control group, using random allocation concealment. Participants and research staff (except intervention staff) will be blinded to group assignment, and additional techniques (e.g., follow-up assessment in some consented, non-randomized participants) will be used to prevent unmasking. It may be difficult to keep assessment research staff blinded to group assignment if participants inadvertently describe their assignment, but all assessment staff will also be blinded to study research questions.

Dependent and Independent Variables (Measurement Techniques)

A summary of all measurement techniques is shown in Table 1.

Baseline Assessment

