Consenting participants will receive a baseline assessment. Data will be collected at two separate visits over a seven day period. At the first visit, research staff will obtain informed consent, complete the first part of the baseline assessment, and provide the Veteran with a wrist actigraph device. Using a process similar to that in our ongoing VA HSRD-funded CBT-I trial, the participant will return after one week with the actigraph

and research staff will complete the second part of baseline assessment. Veterans will receive \$25 for completing the baseline assessment.

Independent assessment research staff not involved in the intervention will perform baseline, post-treatment, and 3- and 6-month follow-up assessments. All research staff will undergo two weeks of structured training, including review of human subjects protection issues, basic interviewing techniques, cultural sensitivity training, and in-depth instruction on data collection instruments and equipment. Procedure manuals have been written for all instruments and equipment. Senior research staff will observe data collection at least quarterly, and inter-rater reliability will be assessed initially and re-assessed annually, and if new research staff are hired. These procedures have resulted in consistent, reliable data collection in our prior work and we have experience with all measures listed.

Data collection methods and instruments were chosen that are appropriate for use in older people. Specific instruments were chosen based on primary and secondary outcomes of interest, key covariates needed for analyses, efforts to minimize participant burden, our prior experience with these measures and published recommendations for standard assessment in sleep research.¹ For ethical reasons, the participant's primary provider will be notified (with the participant's consent) if our assessments identify any serious, unrecognized sleep disorder, or other severe condition (e.g., severe pain, severe depression). Our research team will also follow our established protocol when there is evidence of any serious, life-threatening situation (e.g., suicidality) identified during interactions with participants (see Human Subjects section).

Medical Chart Review (Data Collected by Research Staff)

- Structured clinical review of comorbidity, illness severity, and medications

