Participants will be randomized to one of two groups: 1) intervention group, who will receive an integrated, manual-based individual CBT-I plus PAP adherence behavioral self-management program, or 2) control group, who will receive an attention control condition (general sleep and OSA education). All participants will be prescribed PAP therapy (through the sleep clinic), and will receive their PAP device through the sleep clinic, as described above. The intervention and control conditions will be provided by research allied health personnel (i.e., not psychologists). The active intervention was designed to have a high enough intensity/potency for efficacy, while avoiding as much as possible the risks of excessive participant burden and excessive costs of implementation into routine care if successful. In addition, the intervention is structured and manual-based (i.e., using a concise intervention manual) in order to be highly translatable to routine care. The intervention and control programs will begin after baseline assessment and randomization, and the intervention or control conditions will begin approximately 2 weeks prior to initiation of PAP therapy. If there is a delay in receipt of PAP equipment, participants will receive a weekly phone call from intervention/control staff to monitor progress and provide reinforcement (of information learned in sessions 1 and 2 in the intervention group, and to encourage continued participation in the control group). If the PAP equipment is received prior to completion of sessions 1 and 2, the intervention/control condition will progress as scheduled below over a 6 week period.

Intervention condition

The intervention provides an integrated behavioral approach to OSA and insomnia, which combines a CBT-I treatment for insomnia with an OSA and PAP self-management program. The aspects of each intervention are integrated seamlessly into one intervention program, provided in individual (i.e., one-to-one) sessions with master's level allied health personnel (e.g., health educator) (see Appendix 3 for example of session material). The first two sessions will be timed to occur prior to the patient receiving their PAP equipment; sessions 3 – 5 will occur after the participant receives their PAP device, with session 3 timed to

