Post-treatment assessment: As is traditionally performed in behavioral insomnia interventional studies, “post-treatment” assessments will be repeated soon after completion of the treatment (either intervention or control conditions). Wrist actigraphy will be repeated for 7 days, in addition to the sleep quality (PSQI, ISI, ESS), cognitive functioning tests (HVLT-R, Digit Symbol Substitution, Trails A and B, Forward and Backward Digit Span, Letter-Number Sequencing, COWA), depression (PHQ-9), quality of life (SF-12v2), caregiving questions, process measures (DBAS-16 and Self-efficacy, Knowledge and Decisional Balance Index subscales), and other questionnaires (see Table 4). A blood sample will also be obtained from each participant. In addition, PAP adherence data will be collected as described above.

Three-month follow-up assessment: The main outcome assessment will be performed at three months after baseline assessment, using the same measures included in the post-treatment assessment.

Six-month follow-up assessment: Follow-up assessment will be performed again at 6 months after baseline assessment (to test for maintenance of outcomes), using the same measures included in the post-treatment and 3-month follow-up assessments.

Twelve-month follow-up assessment: Participants will be contacted by telephone after 12-months for a brief interview. Research staff will administer the three sleep questionnaires (ISI, PSQI, and ESS) and PAP adherence data will be collected.

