The analysis plan for each specific hypothesis is listed below. In addition to hypothesis testing to analyze effects of the intervention on sleep, PAP adherence, depressive symptoms and quality of life, we will develop models showing which covariates predict the values of each of the outcome measures. Prior to hypothesis testing, data will be cleaned, possible outliers identified, and data distributions evaluated for assumptions of analysis (e.g. normality, homogeneity of variance). If necessary, normalized rank transformations as described in Bonate²⁴ will be performed and normalized rank scores will be submitted to analysis.

Hypothesis 1: Compared to control participants, participants randomized to the intervention will have improved nighttime sleep (i.e., higher sleep efficiency, better self-reported sleep) and better PAP adherence (measured objectively) at 3-months follow-up.

This hypothesis tests for differences between the intervention and control groups in our primary outcome measures of nighttime sleep and PAP adherence, between baseline assessment and 3-months follow-up, which is our primary time endpoint. Subjective measures of sleep outcomes will include sleep diary (sleep onset latency, wake after sleep onset [WASO], and sleep efficiency) and sleep quality (PSQI). The objective measure of sleep outcome will be actigraphy (sleep efficiency), and the objective measure of PAP adherence will be downloaded from the PAP smart card (percent of nights with PAP use \geq 4 hours, and mean hours of PAP use per night). All outcomes will be assessed using intention to treat analyses. A 2 X 2 (time X group; where time = baseline or 3-month assessment; and group = intervention or control) analysis of covariance analysis will be used with Bonferroni-corrected post-hoc comparisons to investigate differences between the groups in terms of treatment effects in the sleep variables (where baseline and 3-month follow-up data will be available). For PAP adherence outcomes, there will be no “baseline” data (i.e., PAP adherence data isn’t available until the participant starts PAP therapy), so outcomes between groups will be compared with independent samples t-tests and Chi-square test for difference in proportions.

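### The primary 3-month visit is timed from a baseline completed before randomisation, so time since treatment and PAP exposure at that visit vary between participants

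*Combined protocol and SAP*

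**What the plan says.** Under Post-Treatment and Follow-up Assessments, "The main outcome assessment will be performed at three months after baseline assessment". The 6-month visit uses the same anchor: "Follow-up assessment will be performed again at 6 months after baseline assessment". No anchor is given for the 12-month telephone contact. Hypothesis 1 concerns change "between baseline assessment and 3-months follow-up, which is our primary time endpoint".

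Recruitment has two steps. In the first, "We will mail a letter to these Veterans when their referral to sleep clinic is received"; a 7-day opt-out period, a telephone insomnia screen, consent and baseline follow. Baseline itself is spread out: "Data will be collected at two separate visits over a seven day period". In the second step, the invitation to the randomised trial goes to "consented Veterans who have completed baseline testing, are diagnosed with OSA" and who have been prescribed PAP. Randomisation is stratified by AHI below 30 or 30 and above, so it needs the sleep-study result.

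Under Treatment groups, both programmes start after baseline and randomisation, and "the intervention or control conditions will begin approximately 2 weeks prior to initiation of PAP therapy". Table 2 and Table 3 each show five sessions over six weeks. In the intervention arm, sessions 3 to 5 wait for the PAP device. In both arms, late PAP is covered by weekly calls, with no maximum delay. The post-treatment assessment is placed soon after treatment is completed, without a window.

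**The concern.** The post-treatment visit is tied to the end of treatment and the primary visit to baseline. Whatever time passes between baseline and session 1, and any wait for PAP, comes out of the interval between those two visits, and by a different amount for each participant. Nothing in the text available caps the interval from baseline to randomisation, sets a visit window, or says what happens if the two visits meet.

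Three planned analyses are affected:

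- PAP adherence at 3 months is compared by t-test and chi-square, with no stated allowance for time on PAP. Two of its three rows in Table 5 ask for 54 and 62 per group at randomisation, against 60 planned, so there is little room for added variance.
- The PSQI, a Hypothesis 1 outcome, covers the last month. It can therefore describe weeks when treatment was still under way.
- The linear and quadratic change models treat the visits as common time points, although their spacing relative to treatment differs between participants.

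**Working it through.** **Inputs from the documents.** The programme lasts 6 weeks: Tables 2 and 3 list sessions in weeks 1, 2, 3, 4 and 6, which reproduces the stated five sessions over six weeks. PAP starts about 2 weeks after session 1. Post-treatment actigraphy lasts 7 days. PAP use is summarised over the prior 7 days and/or, where appropriate, the prior 30 days.

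**Inputs not in the documents (assumptions).** R = weeks from the first baseline visit to session 1. D = weeks by which late PAP lengthens the programme. Which of the two baseline visits is time zero is not stated; that alone can shift the result by up to a week.

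**Formulas, in weeks from baseline.**

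- 3-month visit: 3 × 365.25 / 12 / 7 = 13.04. 6-month visit: 26.09.
- End of treatment: R + 6 + D. PAP start: R + 2 + D.
- Gap from end of treatment to the 3-month visit: 13.04 - 6 - R - D, about 7 - R - D.
- Weeks on PAP at that visit: 13.04 - 2 - R - D, about 11 - R - D. If the device arrives early the programme keeps its six-week schedule, and PAP exposure is longer than this.

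| R | D | Treatment ends (week) | Gap to 3-month visit (weeks) | Weeks on PAP |
|---|---|---|---|---|
| 1 | 0 | 7 | 6 | 10 |
| 2 | 0 | 8 | 5 | 9 |
| 4 | 0 | 10 | 3 | 7 |
| 6 | 0 | 12 | 1 | 5 |
| 4 | 2 | 12 | 1 | 5 |
| 4 | 4 | 14 | -1 | 3 |
| 8 | 0 | 14 | -1 | 3 |

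**Thresholds for R + D.**

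- A 30-day recall or look-back reaches into the treatment period: above 7.045 - 30/7 = 2.76 weeks.
- The visit overlaps the week of post-treatment actigraphy, if that starts when treatment ends: above 13.04 - 6 - 1 = 6.0 weeks.
- A full 30 days of PAP data is not available: above 13.04 - 2 - 30/7 = 6.8 weeks.
- The visit precedes the end of treatment: above 13.04 - 6 = 7.0 weeks.

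If the 30-day PAP window is used, the share of it lying inside treatment with D = 0 is (4.3 - gap)/4.3: none at R = 2, (4.3 - 3)/4.3 = 30% at R = 4, and (4.3 - 1)/4.3 = 77% at R = 6.

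**Six-month visit.** The gap is 26.09 - 6 - R - D: 19.1 weeks at R = 1, D = 0, and still 8.1 weeks at R = 8, D = 4.

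**The case against.** The strongest reply is that the comparison between arms stays valid. R is fixed before allocation, so it should balance. The clinic staff who supply PAP are blinded to assignment, and both arms follow the same session calendar. The plan also openly defines the visit as three months from baseline and never claims three months after treatment; maintenance is tested separately at 6 months. All of this stands. A reader might infer between-arm bias or an overstated claim of durability, but the documents show neither. The loss of precision cannot be quantified from them either.

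A second reply concerns the size of the lag. The plan reports that "Currently, there is a 3-4 week wait for an ambulatory sleep study; the wait for an in-laboratory study is > 4 weeks". It is tempting to read this as the delay after baseline, but it describes the wait for the study, and recruitment starts at referral. The opt-out period, screening, scheduling and the baseline week use up part of that wait. Baseline probably precedes the sleep study for many participants, but no section says so for all. What is explicit is that baseline precedes invitation, randomisation and session 1.

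Third, a reader might conclude that the primary visit falls before treatment ends. That needs R + D above about 7 weeks. The open-ended laboratory wait and the uncapped PAP delay permit it, but nothing shows it to be typical.

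Finally, the study-design figure is not in the text available, so a window shown only there cannot be ruled out. It would not change the anchor stated in the text.

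**Conclusion.** The point holds as a weakness in how the primary time point is defined. The stated anchor makes time since treatment and PAP exposure differ between participants and shortens both. Under the assumed R of 2 to 6 weeks with no PAP delay, the primary visit comes 5 to 1 weeks after treatment with 9 to 5 weeks on PAP; PAP delay reduces both week for week. At the upper end the visit adds little to the post-treatment assessment.

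For the 6-month visit only the variable anchor applies, because it stays well clear of treatment throughout the range examined. The sizes rest on R and D, which the sponsor can replace with clinic data. The anchor and the order of events rest on explicit text. It is a low-cost improvement worth making before visits are scheduled, not an error that undermines the randomised comparison.

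**What to change.** In the follow-up assessment paragraphs and Table 4, time the 3-, 6- and 12-month assessments and the PAP download windows from the date of randomisation, with a stated visit window. Keep the pre-randomisation assessment as the baseline value. In addition:

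- record time since PAP start at each visit;
- state how a 3-month assessment is handled if late PAP would make it overlap or precede the post-treatment assessment;
- give a nominal anchor date to the consented, non-randomised participants who are followed to protect masking, so that scheduling does not reveal their status.

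If session 1 closely follows randomisation, the gap after treatment becomes about 7 - D weeks whatever R is. Any wait between randomisation and session 1, and any PAP delay, would still shorten it, so some variation remains.

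The cost is wording and scheduling, with each participant's follow-up ending later by the baseline-to-randomisation lag. At the planned 5 randomised per month, 120 / 5 = 24 months of accrual. Adding 12 months of follow-up and an assumed 2-month lag gives 38 of the 42 months in the 3.5-year project, which leaves 4 months for start-up and close-out.
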